Evaluable patients' population (evaluable per protocol population, EPP): consists of all patients from the FAS without any major inclusion/exclusion violation, major dosing violation as defined for phase II part 1, or major protocol conduct violation who were dosed with IMP(s) according to the treatment allocated at randomization and have at least one baseline and one post-baseline evaluable CT-scan at week 6 after start of study treatment with a best overall response assessment different from 'Unknown' according to RECIST 1.1 evaluation criteria.

Sample size:

Phase Ib of the study: there will be no formal sample size for the phase Ib of the study. The dose escalation part of the trial follows the methodology of a 3+3 cohort design for dose-finding studies in oncology. Depending on the observed DLTs, a maximum of 12 evaluable patients will be included in this part of the study.

Phase II part 1: a Simon's two-stage design will be used. The null hypothesis for response rate H_0 is set at 10% corresponding to the response rate observed in second line patients, the alternative hypothesis of efficacy is set at $H_A=25\%$, the type I error α is set at 5% one sided, the type II error β is set at 20% (power=80%). Under these hypotheses and applying a minimax two-stage Simon design, enough patients will be treated to obtain 22 evaluable patients as a first stage. If at least 3/22 patients are considered responders, the enrolment will be continued, otherwise it will be stopped. In the initial design and at the second stage enough patients should have been treated to obtain at least 40 evaluable patients in total. The study would have been considered positive with at least 8/40 responders. With a hierarchical strategy on the final analysis, a subgroup analysis performed in oropharyngeal SCCHN patients and with a null hypothesis for response rate (H_0) set at 10% and the alternative hypothesis of efficacy set at $H_A = 35\%$, 18 oropharyngeal SCCHN patients would have been needed to reach a power of 81% and actual alpha at 2.8%. This analysis would have been considered positive with at least 5 responders among the 18 SCCHN patients. The second stage of the Simon's design has not been done following the decision to exclude oropharyngeal SCCHN and to change to a randomized controlled two-arms study (phase II part 2).

Phase II part 2:

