8 ASSESSMENT OF EFFICACY

- Assessment of efficacy according to RECIST VERSION 1.1

The assessment of efficacy is based on Response Evaluation Criteria in Solid Tumors (RECIST) version 1.1 (Eisenhauer E.A. *et al.*, 2009).

For efficacy evaluation, patients must have at least one measurable lesion by CT/MRI scan (minimum size not less than 10 mm) at baseline and a post-baseline evaluable CT-scan at week 6 after start of study treatment with a best overall response assessment different from 'Unknown' according to RECIST evaluation criteria. However, if a patient progressed or died due to underlying cancer before scheduled scan 6 weeks after study treatment start could be performed, the patient will still be included in the evaluable population.

Tumor assessment will be performed LOCALLY according to investigator's assessment every 6 weeks from the start of study treatment until disease progression or for a period of 9 months after start of study treatment, whichever occurs first. Beyond 9 months after start of study treatment, the evaluations will be performed every 12 weeks until disease progression. The same schedule of tumor evaluation will be applied for patients who stopped the study treatment for any reason other than progressive disease.

For all patients, tumor response assessment will be performed by preferably CT (or MRI) of the head and neck, chest, abdomen and all other known sites of disease (e.g. pelvis, if applicable) and other established assessments of tumor burden if CT/MRI imaging is insufficient for the individual patient. In case of bone pain, an adequate radiological and/or isotopical exploration is to be performed to research metastases. All the scans performed at baseline and other imaging performed as clinically required (other supportive imaging) need to be repeated at subsequent visits.

Per RECIST, the imaging method used at baseline should be matched at all subsequent assessments, but, for a number of reasons such as site error (e.g. switch from MRI to CT) or renal dysfunction (making contrast a risk), this will not always be done. A strict implementation of RECIST would mean that any change in imaging method compared to one used at baseline should lead to unknown overall response at given assessment. However, a change in the use of contrast does not necessarily represent a change in precision since for many tumor types, the assessment can be done despite the fact that contrast has changed.

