Phase II part 1: Evaluable patients' population for tumor response (evaluable per protocol population, EPP): consists of all included patients who were dosed with both IMPs (TG4001 + avelumab) and have at least one baseline and one post-baseline evaluable CT-scan at week 6 after start of study treatment with a best overall response assessment different from 'Unknown' according to RECIST 1.1 evaluation criteria. However, if a patient progressed or died due to underlying cancer before scheduled scan 6 weeks after study treatment start could be performed, the patient will still be included in the evaluable population. Any patient who has a major inclusion/exclusion violation, major dosing violation, or major protocol conduct violation will be excluded from the EPP. Major dosing violation is considered when minimum exposure is not met defined as at least 6 TG4001 injections and 3 avelumab administrations except if patient has progressed or died due to underlying disease before or at the first evaluation. Due to potential abscopal effect when associating radiotherapy and immunotherapy, patients receiving palliative radiotherapy will be analyzed separately. Whatever the reason for withdrawal, except for disease progression and death due to underlying cancer before scheduled scan 6 weeks after study treatment start could be performed, patients considered as non-evaluable for tumor response will be replaced.

Phase II part 2: Full Set Analysis (FAS) will be the primary set for efficacy analyses. It consists of all randomized patients who were administered at least one dose of IMP(s) according to the treatment allocated at randomization.

Evaluable patients' population per protocol (evaluable per protocol population, EPP): consists of all patients from the FAS without any major inclusion/exclusion violation, major dosing violation as defined for phase II part 1, or major protocol conduct violation who were dosed with IMP(s) according to the treatment allocated at randomization and have at least one baseline and one post-baseline evaluable CT-scan at week 6 after start of study treatment with a best overall response assessment different from 'Unknown' according to RECIST 1.1 evaluation criteria.

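### The phase II part 2 per-protocol set requires a week-6 scan but omits the clause, given for part 1 and in Section 8, that keeps patients who fail before it

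*Combined protocol and SAP*

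**What the plan says.** Part 2 EPP. Section 10.1 starts from the full analysis set (FAS), removes major violations, and keeps patients dosed "according to the treatment allocated at randomization and have at least one baseline and one post-baseline evaluable CT-scan at week 6", with a best overall response other than unknown. The synopsis has the same requirement: "who were dosed with IMP(s) according to the treatment allocated at randomization and have at least one baseline and one post-baseline evaluable CT-scan". Neither place adds an exception for patients who fail before the scan.

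Part 1 EPP. Section 10.1 and the synopsis set the same scan requirement, then make an exception beginning "However, if a patient progressed or died due to underlying cancer before scheduled scan 6 weeks after study treatment start could be performed"; such a patient stays evaluable.

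Section 8. The scan requirement is stated for efficacy evaluation with the same exception and no restriction to a phase or part. If progression or cancer death comes "before scheduled scan 6 weeks after study treatment start could be performed, the patient will still be included in the evaluable population".

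Dosing criterion. The part 2 EPP excludes a "major dosing violation as defined for phase II part 1". That rule sets a minimum exposure "except if patient has progressed or died due to underlying disease before or at the first evaluation".

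Role of the set. Sections 10.1 and 10.3.1 make the FAS primary for part 2, with the analyses repeated on the EPP. Section 10.6 leaves the deviations that determine the EPP to the statistical analysis plan, with a data review meeting before the final analysis.

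**The concern.** Two rules in force give opposite answers for the same part 2 patient. Section 8 keeps a patient who dies of the cancer in week 4; the scan criterion in 10.1 removes that patient. Within 10.1 itself, the imported dosing rule spares early failures whom the scan rule then excludes. No reason is given for treating part 2 differently from part 1.

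Taken literally, entry to the EPP depends on a post-randomisation outcome: remaining alive and under assessment long enough to be scanned. Section 7.1 does not allow the first post-baseline scan before 5 weeks of treatment, so a patient who dies earlier would not have a scan that meets the criterion. The patients lost are those with the worst early outcomes, and the loss is unequal if one arm fails sooner. In an open-label trial with local tumour assessment, a conflict left open until the data review meeting could be settled when arm and outcome are known.

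**Working it through.** **Inputs**
- Planning median PFS: 2.0 months (avelumab alone) and 4.5 months (combination); synopsis and Section 3.2.
- About 80 patients, 40 per arm; Section 10.2.
- Week 6 = 42/30.4375 = 1.380 months. The definitions page equates start of study treatment with randomisation in part 2, so this clock matches the PFS clock.
- Share f of pre-week-6 events that leave no evaluable scan: not in the documents. Assumed range 10% to 50%.
- Exponential PFS: assumed.

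**The plan's own figure.** HR = 2.0/4.5 = 0.444. Freedman's formula at one-sided 5% and 95% power: [(1+0.444)/(1−0.444)]² × (1.645+1.645)² ≈ 6.76 × 10.82 ≈ 73.2, so 74 events. Section 10.2 states 76, and 74 for its favourable zone. The planning inputs are therefore read correctly; no figure in the plan is disputed here.

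**Step 1: events before week 6.** p = 1 − exp(−ln 2 × 1.380/median).
- Control: 1 − exp(−0.478) = 38.0%, or 15.2 of 40.
- Combination: 1 − exp(−0.213) = 19.1%, or 7.7 of 40.
- At 5 weeks (1.150 months): 32.9% and 16.2%.

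These shares are upper bounds on exclusion. RECIST progression is found by scanning, so most of these events would be recorded on the week-6 scan, and those patients stay in the EPP.

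**Step 2: patients excluded.** Share excluded = f × p.

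| f (assumed) | Control | Combination | Events lost per 80 patients |
|---|---|---|---|
| 10% | 3.8% (1.5 of 40) | 1.9% (0.8 of 40) | 2.3 |
| 25% | 9.5% (3.8 of 40) | 4.8% (1.9 of 40) | 5.7 |
| 50% | 19.0% (7.6 of 40) | 9.6% (3.8 of 40) | 11.4 |

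**Step 3: response rate.** If those excluded are non-responders, apparent ORR = true ORR/(1 − share excluded). With a true ORR of 20% in both arms:
- f = 10%: 0.20/0.962 = 20.8% control; 0.20/0.981 = 20.4% combination.
- f = 50%: 0.20/0.810 = 24.7% control; 0.20/0.904 = 22.1% combination.

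The apparent difference moves against the combination by up to about 2.6 points.

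**Step 4: medians.** When the EPP median falls after week 6, it equals median × [1 + log₂(1/(1 − share excluded))].
- f = 10%: 2.0 × (1 + 0.056) = 2.1 months; 4.5 × (1 + 0.028) = 4.6 months.
- f = 50%: 2.0 × (1 + 0.304) = 2.6 months; 4.5 × (1 + 0.146) = 5.2 months.
- Limiting case, all excluded: 1.38 + 2.0 = 3.4 months and 1.38 + 4.5 = 5.9 months.

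**Step 5: hazard ratio.** A simulation with 5,000 patients per arm and exponential PFS gave a Cox HR of 0.443 with no exclusion and 0.437 to 0.453 when 10% to 100% of pre-week-6 events were dropped. No systematic shift is visible.

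**The case against.** The strongest reply is that 10.1 is silent rather than contrary. Section 8 has no phase limit and elsewhere addresses part 2 by name, and the imported dosing rule spares early failures, so the intention was probably to keep them. That is a fair reading of intent, and it is why the remedy is a harmonising sentence and not a change of design. It does not remove the conflict: 10.1 defines the analysis sets, states the exception for part 1 and not for part 2, and a programmer working from it would exclude these patients. Nor can Section 8's evaluable population be read as the FAS, the only set that the definitions page lists under evaluable patients for part 2, because the FAS has no scan requirement.

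It can also be said that few patients would be affected. Entry requires ECOG 0 or 1 and a life expectancy of at least 3 months, scans have a window of 7 days either side, and Sections 4.3.2 and 8 ask for every effort to document progression after clinical deterioration. This stands, and it is why the 38% and 19% are only ceilings and the range starts at 10%.

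A further point is that the imported minimum of 6 TG4001 injections, read literally, cannot be met in the avelumab-alone arm. That is a separate defect. The percentages above isolate the scan criterion and presuppose that the dosing rule is applied workably in that arm.

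A reader might infer more than this. One inference is that the primary result is biased, since 10.4.2 opens by naming the EPP for efficacy without a phase limit. But 10.1 and 10.3.1 make the FAS primary for part 2, and 10.4.2 itself places the primary log-rank test there. Another is that the omission flatters the combination. Under the planning medians the control arm loses more early failures, so the bias in response rates runs the other way.

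**Conclusion.** The point holds as a conflict in the definition of a supportive analysis set. As written, the part 2 EPP removes patients whom Section 8, the part 1 definition and the imported dosing exception would all keep. The primary FAS log-rank test is untouched, and the EPP hazard ratio would move little under proportional hazards. What would be distorted is the EPP medians, ORR and DCR, the event count and the comparability of the arms.

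The size rests on the planning medians, exponential PFS and an assumed 10% to 50% of early events without an evaluable scan. The ORR figures also take a true rate of 20% in both arms and no responders among those excluded. On that basis about 4% to 19% of control and 2% to 10% of combination patients would be lost. The documents do not give the number of patients without a week-6 scan, and they do not fix the direction of any hazard-ratio bias if hazards are not proportional. The change should be made because the contradiction is plain and cheap to remove.

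**What to change.** Copy the Section 8 exception in full into the part 2 EPP definition, both in 10.1 and in the synopsis. It is the sentence that ends "the patient will still be included in the evaluable population". Keep its limit to deaths from the underlying cancer. Wording that admits every early death would go beyond both Section 8 and part 1.

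State that patients kept by this clause count as non-responders for ORR and as not controlled for DCR. Leave the PFS definition in 10.3.1 unchanged (RECIST 1.1 progression or death from any cause), so that a clinical progression without RECIST documentation does not become a PFS event through this change.

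If the sponsor does intend a different rule for part 2, the alternative is to restrict the Section 8 exception to part 1 and justify the difference. Either way, settle it before the data review meeting. The cost is one sentence in two places plus a line on how these patients are counted; no new data are needed.

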10.2. Determination of sample size

In the phase Ib part of the study, 3 to 6 evaluable patients will be included and treated at each selected dose level. Should the results of this first part of the study show an acceptable safety profile of the combination, accrual in the phase II part of the study will start.

Phase II part 1: A Simon's two-stage design was used. The null hypothesis for response rate (H_0) is set at 10%, corresponding to the response rate observed in second line patients, the alternative hypothesis of efficacy is set at $HA = 25\%$, the type I error α is set at 5%, the type II error β is set at 20% (power = 80%). Under these hypotheses and applying a Minimax two-stage Simon design, enough patients will be treated to obtain 22 evaluable patients in the first stage. If at least 3/22 patients are considered responders, the enrolment will be continued, otherwise it will be stopped. In the initial design and at the second stage enough patients should have been treated to obtain at least 40 evaluable patients in total. The study would have been considered positive with at least 8/40 responders. With a hierarchical strategy on the final analysis, a subgroup analysis performed in oropharyngeal SCCHN patients and with a null hypothesis for response rate (H_0) set at 10% and the alternative hypothesis of efficacy set at $HA = 35\%$, 18 oropharyngeal SCCHN patients would have been needed to reach a power of 81% and actual alpha at 2.8%. This analysis would have been considered positive with at least 5 responders among the 18 SCCHN patients. The second stage of the Simon's design has not been done following the decision to exclude oropharyngeal SCCHN and to change to a randomized controlled two-arms study (phase II part 2).

The final ORR analysis will be performed 24 weeks after last patient-in.

Phase II part 2:

The primary objective is to compare the PFS of TG4001 in combination with avelumab vs avelumab alone in patients with R/M HPV-16 positive advanced malignancies and without liver metastases at baseline. PFS will be evaluated based on RECIST 1.1.

Patients without liver metastases at baseline:

Efficacy will be evaluated by comparing the PFS between monotherapy arm (avelumab alone) and combination arm (TG4001 and avelumab) with an adaptive approach.

With an one-sided type I error α at 5%, 76 events are needed to reach a power of 95%. This should happen after around 80 patients enrolled (40 patients per arm). Assuming 5% drop-out in each arm, 84 patients will be randomized.

[figure not shown]
Due to the uncertainty on the true treatment effect and data variability, and to reduce the risk of running an underpowered study, it is considered appropriate to adopt an adaptive approach for the sample size. This will offer a mechanism to adjust the sample size in response to treatment effect and variability estimates seen at a planned interim analysis.

The interim analysis will be conducted after 37 events which will occur approximately 16 months after the inclusion of the first patient. At that time, it is estimated to have around 50 patients enrolled. Based on the results of the interim analysis, sample size re-estimation will be performed. According to simulations on CHW (Cui, Hung and Wand) approach using EAST 6.5., the proposal is as follows:

- Start with a fixed sample size calculation based on the primary endpoint.
- Based on the interim analysis result maintain or increase the sample size in order to obtain the desired power of 90%.

Conditional power will be calculated based on the interim results. Should the conditional power be in the favorable or unfavorable range the sample size and the number of events will not be adjusted and will remain at the initial sample size. Conditional power falling into the promising zone will have a sample and events increase. The regions and their implications on sample size are detailed below:

- **Favorable:** If the interim results are sufficiently favorable corresponding to a CP of more than 90%, final analysis will be performed on 74 PFS events corresponding to an estimated sample size of 80 evaluable patients. This will occur approximately 26 months after the inclusion of the first patient.
- **Promising zone:** If the interim results are equivalent to a CP between 90% and 30%, the sample size will be recalculated according to the median PFS observed in the two arms with a cap of 2 times the initial events.
- **Unfavorable zone:** If the interim results are not favorable corresponding to a CP between 30% and 10%, the trial may continue up to the initial sample size of 80 patients or could be stopped
- **Futility:** If the interim results are futile corresponding to a CP lower than 10%, the trial will be stopped for futility at the interim analysis.

Assuming an uniform enrollment with 3 patients per month and based on simulations, in case of sample size reassessment, an average of 124 events would be needed (corresponding to 136 patients). Assuming a 5% lost to follow-up or withdrawal of consent rate, a total of 142 patients should be randomized to the 2 treatment arms in a 1:1 ratio (71 patients in each treatment arm). Based on the aforementioned assumptions, a power of 70% is expected using an unstratified log-rank test at a 1-sided cumulative 5% level of significance. [REDACTED]

[REDACTED]

[REDACTED]

[REDACTED]

[REDACTED]

Full details of the adaptive method for sample size specified above will be given in the Statistical Analysis Plan (SAP).

Patients with liver metastases at baseline:

A sample size of [REDACTED] is planned.

[REDACTED]

[REDACTED]

[REDACTED]

[REDACTED]

10.3. Study endpoints

10.3.1. Primary endpoint

Phase Ib: Dose limiting toxicities defined as follows:

- Grade ≥ 3 drug related adverse event. However, fatigue, nausea/vomiting adequately treated with anti-emetics, endocrinopathies adequately controlled with one physiologic hormone replacement, skin toxicity and single laboratory values out of normal range without any clinical correlate, asymptomatic grade ≥ 3 lipase or amylase elevation, tumor flare defined as local pain, irritation, or rash localized at sites of known or suspected tumor or a transient Grade 3 infusion adverse event are excluded
- Liver function test abnormality:
 - o AST or ALT $> 5 \times$ ULN
 - o Total bilirubin $> 3 \times$ ULN
 - o Concurrent AST or ALT $> 3 \times$ ULN and total bilirubin $> 2 \times$ ULN
- Drug related adverse event requiring treatment interruption for more than 2 weeks

The RP2D will be defined as the dose at which less than 33% of the patients (0 or 1 patient among 6 evaluable patients) experience a DLT.

Dose limiting toxicities will be assessed during the first 4 weeks of the combination and will be graded according to NCI CTCAE version 4.03.

To be evaluable for the primary objective of the phase Ib of the study, patients must complete the first 4 weeks of the combination or discontinue before the end of the 4 weeks for a DLT. Patients must receive at least one dose of both IMPs (TG4001 + avelumab) and have at least one valid post-baseline safety assessment. The statement that a patient had no AE, on the Adverse Events eCRF page, constitutes a valid safety assessment. The occurrence of death also constitutes a valid safety assessment. Patients who are not evaluable for phase Ib safety analysis or are withdrawn for other reasons than toxicity, will be replaced.

The DLT population will be the primary population for analyses. These analyses will be repeated on the SAF.

Phase II part 1: The primary endpoint of the phase II part 1 is the Overall Response Rate (ORR by RECIST 1.1 criteria).

The EPP will be the primary population for efficacy analyses in the phase II part 1. These analyses will be repeated on the SAF.

The best response will be recorded from the first study drug administration until documented disease progression. A PR or CR must be confirmed at a subsequent evaluation at least 4 weeks apart.

Phase II part 2: The primary endpoint of phase II part 2 is PFS by RECIST 1.1 criteria. The FAS will be the primary population for efficacy analyses in the phase II part 2. These analyses will be repeated on the EPP.

Progression Free Survival (PFS) is defined as the time from the date of randomization to the date of first documented tumor progression or death due to any cause, whichever occurs first. If a patient has not had a PFS event at the cut-off date for analysis or at the date when a further antineoplastic therapy (other than those planned as study treatment in the protocol) is started, PFS will be censored at the date of last evaluable tumor assessment before the cut-off or start of further antineoplastic therapy.

